Obtaining human tissue for basic research or biospecimen bank

Survey instrument

None of the above

The following documents are currently attached to this item:

There are no documents attached for this item.

Department budget code

None

Multi-Site Research

Other Sites

No other sites

Management of Information for Multi-Center Research

n/a

The following documents are currently attached to this item:

There are no documents attached for this item.

Protocol

Abstract

Of the many factors contributing to the obesity epidemic, the timing of food consumption is now recognized as a significant contributor to body weight regulation. Disruption of the normal timing of feeding in mice has been found to promote weight gain, alter serum leptin levels, and induce hypothalamic leptin resistance. Delays in daytime eating have also been found to increase the risk of obesity and metabolic syndrome in humans. Disrupting normally-timed sleep-wake cycles produces major effects on body weight, adiposity, and metabolism, but it remains unclear whether meal timing independently plays a causal role in metabolic dysregulation when sleep-wake cycles are unaltered. The purpose of this study is to determine if, controlling for eating and sleep timing, caloric intake, and exercise, daytime vs. delayed eating affects body mass, adiposity, and energy metabolism in healthy adults.

Objectives

Overall objectives

To determine if timing of food consumption (daytime vs. delayed eating) affects body mass, adiposity, and energy metabolism by enrolling 30 healthy men and women in a randomized cross-over design study.

Primary outcome variable(s)

To determine if timing of food consumption (daytime vs. delayed eating) affects body mass (kg) after a period of two months.

Secondary outcome variable(s)

Our secondary outcomes will be assessed before and after each eating condition for a total of four assessment periods. Blood samples will be taken every four hours for 24 hours in the CTSC during each assessment. Metabolic testing and DEXA will occur once at each of the four assessment periods. Specific secondary outcomes include: Amplitude and phase of circadian rhythms of leptin, cortisol, and melatonin; Fasting levels of glucose, insulin, adiponectin, cholesterol, triglycerides, and non-esterified fatty acids; Energy expenditure and fuel oxidation as measured by indirect calorimetry; and Body composition measured using DEXA

Background

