[name], the Principal investigator, will be responsible for the overall conduct of this research. Along with [name], co-investigators [name], an expert in circadian rhythms and [name], PhD, an endocrinologist who will serve as medical director. [name], will serve as admitting physician for the study. Additional staff available include the research coordinator ([name]) who will be responsible for recruitment, initial screening, study logistics, and delivery of food; [name], MPH, Co-Medical Director at CWED will be available for any medical issues that arise and reviewing DXA scans. CTRC services will also be involved, including [name] at the metabolic kitchen and nursing staff for support of the 24 hour inpatient assessments. Metabolic testing will also occur at the CTRC in concert with [name] resources in Experimental Psychiatry. [name] will perform the metabolic testing, as she has in previous studies. Our offices at the Center for Weight and Eating Disorders are adequate for recruitment and screening of the participants. We will also use the CTRC at Presbyterian Hospital. It houses a DEXA machine that will be used at each of the pre-post eating condition assessments. We will recruit our 30 participants from within the UPenn and West Philadelphia community so they are in close proximity to receive the food that we will supply. These will be healthy controls with a BMI of 19 - 30 kg/m². We believe that this goal is feasible within the two-year research window. The PI (a clinical psychologist) or co-I [name] (a physician) will be able to refer the participants to appropriate medical or psychological services as needed.

Characteristics of the Study Population

Target population

Thirty adult participants ages 21-50, BMI of 19-30 kg/m² and stable weight (+/- 10 lbs) over the previous 6 months with access to a personal smart phone, tablet, or other electronic device and who live/work within a 5 mile radius of the Hospital of UPenn.

Subjects enrolled by Penn Researchers

30

Subjects enrolled by Collaborating Researchers

0

Accrual

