Between UPenn, Penn Medicine, and the population of West Philadelphia, an adequate pool of adults live/work within 5 miles of the Hospital of UPenn. PI [name] recently completed a survey of 201 patients at an obstetrics clinic at Penn Medicine and found 91% had texting access and 79% had a smartphone. Thus, we do not anticipate any problem recruiting 30 healthy adult participants within our inclusion criteria.

Key inclusion criteria

Adults of all races and ethnicities; Age 21-50; BMI 19-30 kg/m²; stable weight (+/- 10 lbs) over the previous 6 months; Women must be pre-menopausal with regular menstrual cycles.

Key exclusion criteria

Regular exercise more than 4 d/wk, for 60 min measured by exercise logs and actigraphy; normal activity levels are required throughout the study (+/-30 min/wk of baseline level). Unstable, serious medical conditions; use of medicine linked to weight gain/loss; cancer, diabetes, or autoimmune disease; use of illicit drugs, melatonin, diuretics or hypnotics; current weight loss program; presence of a sleep disorder (determined by surveys and actigraphy); night shift work; extreme chronotypes (extreme larks or night owls); habitual waking outside of 0600 h-0900h; habitual bedtime outside of 2200h to 2400H; and sleep duration outside of 6.5 to 8.5 h/night. Psychiatric exclusions will be depression (Patient Health Questionnaire-9 score 9), lifetime bipolar disorder, psychosis, or lifetime eating disorder; or any other severe psychiatric disorder judged to interfere with study adherence as assessed by the MINI International Neuropsychiatric Interview version 6.0.0. Participants must be non-smokers. Participants will be excluded if they are pregnant. A urine pregnancy test will be conducted during the study screening visit. A urine drug test will also be collected at the screening visit.

Vulnerable Populations

Children Form

Pregnant women (if the study procedures may affect the condition of the pregnant woman or fetus) Form

Fetuses and/or Neonates Form

Prisoners Form

Other

None of the above populations are included in the research study

The following documents are currently attached to this item:

There are no documents attached for this item.

Populations vulnerable to undue influence or coercion

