
The following documents are currently attached to this item:

Procedures (appendixastudytimeline4.14.14.docx)

Procedures (appendix-dailytextquestionsforadherence.docx)

Procedures (appendixcsamplemenu.doc)

Procedures (exitsurveys-draft_6.30.16.docx)

Deception

Does your project use deception?

No

Analysis Plan

All continuous variables will be analyzed using linear mixed-effects model analysis allowing for assessment of the eating condition effect on each continuous outcome of interest while controlling for effects of other covariates such as period, sequence, and a random subject effect nested within sequence. Separate models will be generated for each of the outcome measures, with each outcome measure regressed on eating condition assignment, along with baseline outcome and any other covariates deemed prognostic in preliminary analyses, including adherence measures such as sleep and eating timing, and exercise. The linear mixed-effects models will incorporate adjustments for any period effect and include dropout data. The model will include subject-specific intercepts as random effects, and assumes independent and identically distributed random errors within subject. Analysis of the circadian amplitude and phase of hormonal data will use linear mixed effects cosinor analysis, which accounts for systematic inter-individual differences. Changes in circadian phase and amplitude by condition will be compared with 2-sided t-tests. Mixed-effects models will be analyzed using the SAS PROC MIXED procedure (version 9.3, SAS Institute, Cary, NC). Study coordinators will attempt to minimize missing data. Yet, we anticipate an 80% completion rate (n=16), so intent-to-treat principles will be used. As there are limited data for similar studies, the drop-out rate is based on weight loss studies at UPenn and on a Mediterranean diet study in which retention at 6 mo was 80%.The PROC MIXED procedure allows use of all available data for participants.

The following documents are currently attached to this item:

There are no documents attached for this item.

Are you conducting research outside of the United States?

No

Data confidentiality

- Paper-based records will be kept in a secure location and only be accessible to personnel involved in the study.
- Computer-based files will only be made available to personnel involved in the study through the use of access privileges and passwords.

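### Does the unnamed period-2 baseline visit for body mass call for a two-term baseline in the primary model?

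*Combined protocol and SAP*

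**What the plan says.** The primary question is whether meal timing "affects body mass (kg) after a period of two months". Under Procedures there are four assessments: baseline, after condition 1, after the two-week wash-out, and after condition 2 (A1 to A4 below).

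The Analysis Plan uses a linear mixed model with condition, period, sequence and a random subject intercept, "with each outcome measure regressed on eating condition assignment, along with baseline outcome". It "assumes independent and identically distributed random errors within subject". One baseline term is named, with no visit attached for period 2. Other covariates found prognostic may be added, including adherence measures.

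The text leans towards A1 for body mass. A1 is the only assessment called baseline, and A3 is identified by the wash-out it follows. The wording that points to a pre-post comparison within each period concerns other outcomes:

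- Secondary outcome variable(s): "Our secondary outcomes will be assessed before and after each eating condition for a total of four assessment periods".
- Resources necessary for human research protection, on DEXA: "It houses a DEXA machine that will be used at each of the pre-post eating condition assessments".
- Analysis Plan, on the hormone rhythms: "Changes in circadian phase and amplitude by condition will be compared with 2-sided t-tests".

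**The concern.** In a two-period cross-over with a starting value before each period, the choice of baseline changes the estimator. If it is A1 in both periods, the covariate is constant within a person and the period-2 starting mass gets weight 0. If it is A1 then A3 in one column, the wide spread of body mass between people drives the common slope to about 1. Neither weight responds to how well A3−A1 predicts A4−A2.

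This is the primary outcome, about 16 completers are expected, and the documents give no within-person variance or correlation. The less suitable weight could therefore cost about half the information. An unnamed visit also leaves room to choose after seeing both answers. A two-term baseline looks like cheap insurance: it needs no new visit and one degree of freedom.

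**Working it through.** **The plan's figure.** The Analysis Plan expects 80% completion, n=16. This matches the 20 randomised in the Data and Safety Monitoring section (20 × 0.80 = 16), not the 30 stated elsewhere (30 × 0.80 = 24). I use n = 16, eight per sequence.

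**Set-up.** Let d = A4−A2, c = A3−A1 and ρ = corr(c, d). I assume that body mass is recorded at every assessment (weighing is listed explicitly only at screening) and, at first, that wash-out is complete. Further covariates are left out.

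- A1 reading: Var = Var(d)/n
- Period-specific, slope about 1: Var = [Var(d) + Var(c) − 2Cov]/n
- Two-term: Var = [Var(d) − Cov²/Var(c)]/n × [1 + 1/(n−4)]

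The last factor is 13/12 at n = 16, and √(13/12) = 1.041. In simulation of the planned model with a between-person SD of 10 kg (assumed), the median period-specific slope was 0.99 to 1.00 in nine within-person patterns. With an SD of 3 kg, checked in one pattern, it was 0.95. The stated weights are therefore right.

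**Relative standard errors.** With Var(c) = Var(d) these are 1, √[2(1−ρ)] and √[(1−ρ²) × 13/12]:

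| ρ | A1 | Period-specific | Two-term |
|---|---|---|---|
| 0 | 1.00 | 1.41 | 1.04 |
| 0.15 | 1.00 | 1.30 | 1.03 |
| 0.47 | 1.00 | 1.03 | 0.92 |
| 0.73 | 1.00 | 0.73 | 0.71 |

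The two-term form beats A1 only when ρ² > 1/13, that is |ρ| > 0.28.

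**What ρ might be.** Take visits at 0, 8.7, 10.7 and 19.4 weeks.

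- *Independent errors.* c and d share no assessment. If the plan's error assumption also holds for the starting values, ρ = 0 and A1 is optimal.
- *Random walk* (assumed SD 1 kg per period, measurement SD 0.4 kg). Only the two wash-out weeks overlap. Cov = 2/8.7 = 0.230 and Var = 10.7/8.7 + 2 × 0.16 = 1.550, so ρ = 0.15. A1 is still best.
- *Persistent individual trend.* The eligibility limit is "stable weight (+/- 10 lbs) over the previous 6 months". Read it as ±2 SD of trend: 10 lb = 4.54 kg, 4.54 × 8.7/26.1 = 1.51 kg per period, so SD = 0.76 kg. The trend variance in c and d is (0.76 × 10.7/8.7)² = 0.874. With measurement SD 0.4 kg, ρ = 0.874/(0.874 + 0.32) = 0.73. With 0.7 kg, ρ = 0.874/(0.874 + 0.98) = 0.47.

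Only the third pattern makes A1 costly, and both its inputs are assumptions. An entry limit on past free-living weight is not evidence of a trend on a supplied isocaloric diet.

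**Incomplete wash-out.** Let the true effect be 1 kg, with a fraction f present at A3 and still present at A4. Delayed-first gives mean d = f−1 and c = f; daytime-first gives d = 1 and c = 0. With weight w on c, the expected estimate is 1 − f(1−w)/2.

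- f = 0.5: w = 0 gives 0.75 and w = 1 gives 1.00.
- f = 1: w = 0 gives 0.50 and w = 1 gives 1.00.

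Under independent errors the two-term weight averages 0, so the two-term estimate has the same bias as A1. With mean-reverting mass the weight can be negative: w = −0.16 gives 1 − 0.25 × 1.16 = 0.71 at f = 0.5, outside both readings. If instead half is present at A3 but almost none at A4, w = 0 gives about 1.00 and w = 1 about 1.25, so the change score is not always safe either.

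The 4% cap also fails, because c now differs between sequences by f. The two-term variance relative to A1 becomes 1 + [Var(c)/16 + (f/2)²] × 16/[12 Var(c)]. With error SD 0.5 kg, Var(c) = 0.5:

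- f = 0: 13/12, SE ratio 1.04
- f = 0.5: 1.25, SE ratio 1.12
- f = 1: 1.75, SE ratio 1.32

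At f = 0.5 the A1 standard error is √(0.5/16) = 0.177 kg and the two-term one is 0.177 × 1.118 = 0.198 kg. Root mean squared errors are √(0.25² + 0.177²) = 0.306 for A1, √(1.0/16) = 0.250 for period-specific (no bias) and √(0.25² + 0.198²) = 0.319 for two-term. The proposed primary model is then the worst of the three.

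**The case for a change.** The strongest case for change does not rest on guessing ρ. The bracket in the two-term variance is the minimum over all weights, so without carry-over its standard error is at most 4.1% above the better reading, whatever the within-person covariance. Against that, 16 completers analysed with the period-specific form at ρ = 0 are worth 16 × (13/12)/2 = 8.7 under the two-term form. With A1 at ρ = 0.73 they are worth 16 × 0.711² = 8.1. A small premium against a possible halving looks like a good bargain, and naming the model now would close a choice on the primary outcome.

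The algebra stands, and so does the observation that the visit is not named. The bargain does not hold up as a general one. The premium is capped only if mass has returned by A3, and two weeks may not be enough for that. A3 follows condition 1, so adjusting for it with a weight estimated from about 16 people makes the target depend on nuisance covariances whenever some effect persists. Nor would fixing the baseline close off later choices, because the same section lets prognostic covariates be picked in preliminary analyses.

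**Conclusion.** The gap in wording is real, but it does not call for a change to the plan. A loss under either reading is not shown. On the reading the documents favour, with independent errors extended to the starting values, A1 is optimal and the two-term form is about 4% less precise; with random-walk mass it is about 3% less precise. The period-specific reading would have a standard error 41% larger at ρ = 0, but the documents support it mainly for other outcomes. A material loss under A1 appears only with ρ well above 0.28, which here needs an assumed persistent trend.

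Replacing the primary model would trade precision against carry-over bias, and reasonable statisticians would differ on it. Naming the visit is a detail that an analyst settles before the model is run; the other form can be shown beside it. These conclusions assume 16 completers, body mass recorded at all four assessments, equal variances of c and d in the table of relative standard errors, and no period-varying covariates.

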After an initial phone screen to determine eligibility and assess availability, the screening visit will be scheduled. Study staff will complete a clinical interview assessing typical eating and sleep patterns, weight history, and psychiatric status. Participants will undergo a medical history and physical, and their weight, height, and waist circumference will be measured. Participants will receive logs to record food, physical activity (detailing deliberate bouts of exercise), and sleep-wake, as used in our previous studies of NES, and an actigraph to wear for 10d. Upon completion they will return the completed logs and actigraphs. If they meet the inclusion criteria after this 10d screening period, they will be scheduled to undergo a history and physical at the CTRC and, subsequently, their baseline assessment and randomization. After the 28-h baseline assessment, participants will be randomized to begin the study with either the daytime or delayed eating condition, and they will receive their first 3d of food. The participants will also receive food, sleep, and exercise logs and actigraphs, which they will use for the study duration. Assessments will be conducted at four points: 1) baseline; 2) after completion of condition 1; 3) after the 2 wk wash-out period; and 4) after completion of condition 2. Each assessment will include 28h at the Clinical and Translational Research Center (CTRC) where participants will eat according to their typical schedule (for points 1 and 3) or their assigned schedule - daytime or delayed (for points 2 and 4). 10mL (2 teaspoonfuls) of blood will be drawn at 4h intervals (0800h, 1200h, 1600h, 2000h, 2400h, and 0400h) to measure amplitude and phase of circadian rhythms of leptin, cortisol, and melatonin. Fasting levels of glucose, insulin, adiponectin, cholesterol, triglycerides, and non-esterified fatty acids (NEFAs) will be measured at the beginning of each assessment session. All blood assays will be performed by [name]. and her staff at the RIA Core Lab of the Penn Diabetes Center. Energy expenditure measurement: On the morning after blood draws and an overnight fast, indirect calorimetry will be used to assess energy expenditure and fuel oxidation (respiratory quotient). One technique for assessing energy expenditure involves measuring a proxy of heat loss using indirect calorimetry. The body's energy production is dependent on oxygen (O₂) and each liter of O₂ consumed by the body is equivalent to ~5 kcal; therefore, O₂ consumption (VO₂) provides an accurate indirect way of measuring a person's energy expenditure (Leonard, 2012). In addition to VO₂, the respiratory quotient (the ratio of CO₂ production (VCO₂) to VO₂), can be measured. Because the caloric equivalent for each liter of O₂ consumed varies as a function of respiratory quotient, both measurements are required to calculate resting metabolic rate. Diet induced thermogenesis represents the increase in energy expenditure above resting metabolic rate divided by the energy content of the food ingested and is commonly expressed as a percentage. In this study, a Parvo Medics True One 2400 Metabolic Monitor will be used to measure indirect calorimetry. The metabolic monitor is a compact, integrated metabolic measurement system which contains O₂ and CO₂ analyzers, a device for measuring breathing (ventilation) rates, a gas sampling system, and a computer interface that allows for the transfer of raw data. A canopy/hood interface is used to collect air samples. This metabolic monitor has been widely used in clinical and experimental settings and has been validated (Bassett et al., 2001; Cooper et al., 2009). The metabolic monitor will assess indirect calorimetry for each subject a total of 4 times (once during each inpatient assessment). During each of the four assessments, subjects resting metabolic rate will be assessed the morning after continuous blood draws with each measurement lasting 45 minutes (10-15 minute adaptation period, followed by 30 minutes of testing). During the

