
tests, each subject lays supine in bed with his/her head under a plastic canopy which collects the expired air and is told to remain silent and still and to breathe normally. Resting metabolic rate will be measured after a 10 h overnight fast. These metabolic measurements using indirect calorimetry are routinely conducted (and have IRB approval) for our experimental sleep studies (under Co-I [name] leadership). Body composition will then be measured using DEXA at the Presbyterian Hospital CTRC and will be reviewed by study personnel (i.e., our study's medical director, Co-I [name], or Drs. [name] or [name]). The scans will take approximately 30 minutes, during which time the participants lie flat and still. Participants will receive their food and released at the completion of this assessment. None of these assessment would be considered part of standard care as these are healthy participants. All assessments are performed exclusively for research purposes. [name] will serve as the medical director of the study and [name] will be available for urgent issues during assessments. Research staff will deliver meals and snacks from the CTRC metabolic kitchen every 3d, pick up uneaten food, and collect and provide new actigraphs (1/wk). Personalized menus will accompany the meals and participants will check off each food item they consume and note any modifications to their meals and snacks. The CTRC staff will provide portion size training at baseline, and all participants will receive measuring cups. Participants will purchase their own beverages and record them on the menus. Mean beverage intake, as reported at baseline, will be factored into each participant's total daily caloric and macronutrient totals. CTRC staff will provide a diet consisting of approximately 55% carbohydrate, 15% protein, and 30% fat with an isocaloric energy level. These parameters will remain constant across conditions. Staff will send daily queries by text or e-mail to monitor adherence to the eating, sleep, and exercise parameters (Appendix B) and intervene the same day if participants report consuming less than 80% (4/5) of the provided meals and snacks, eating or sleeping outside of the assigned time windows, or exercising more than prescribed. Staff will also download actigraphy data and collect the logs weekly, to monitor compliance. If participants are unable to consume a meal or snack as provided, they will send a picture of their meal or snack using an electronic device, including a reference object, i.e., a card of known dimensions provided by the investigators to orient the staff to the portion size. This template-based approach has been used to develop more sophisticated mobile applications for food intake assessment. All uneaten food will be saved and returned to the metabolic kitchen when staff delivers new food. If it is not possible to save leftover food, participants will take a picture of the remaining food including the reference object. Kitchen staff will pre-weigh all provided items and post-weigh any non-eaten items and compute macronutrient and caloric counts for participants daily intake using the Nutrition Data System for Research (NDSR). [Note: participants will be provided a master meal and snack menu from which they can pick foods that they find acceptable. If participants do not like certain foods, they can alter their selections. Regular contact with participants due to the scheduled food deliveries and daily queries will facilitate these requests. We plan to offset the high study burden by enrolling participants in close proximity to the CTRC, providing them with all meals and snacks for a total of 4 mo at an estimated value of \$1000, and compensating them \$300 for each of 4 CTRC assessments, with a \$300 bonus at study completion (\$1500 total, paid by check). After the first condition (2 mo), participants will complete assessment 2. They will eat according to their usual (baseline) dietary pattern for two weeks, which serves as a wash-out period from the first assigned eating condition. Participants will then complete assessment 3, immediately followed by completion of the second eating condition, followed by assessment 4. All assessments follow the same protocol. Following completion of the fourth assessment, participants will complete a brief survey regarding their perceived adherence to study protocol and explain what they would have changed to make the study easier to adhere to. Appendix A shows the study timeline. Appendix B shows the text/email questions we will use to assess adherence each day. Appendix C shows a sample menu that will be used for participants to identify their food preferences.

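### The only model for body mass allows adjustment for post-randomisation adherence, including eating timing, which is the randomised factor

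*Combined protocol and SAP*

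**What the plan says.** The primary outcome is stated as "To determine if timing of food consumption (daytime vs. delayed eating) affects body mass (kg) after a period of two months". Under Procedures, "participants will be randomized to begin the study with either the daytime or delayed eating condition", so the timing of eating is the randomised factor.

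The Analysis Plan has a single specification: "All continuous variables will be analyzed using linear mixed-effects model analysis allowing for assessment of the eating condition effect", "controlling for effects of other covariates such as period, sequence, and a random subject effect nested within sequence". Baseline outcome is added to this, along with "any other covariates deemed prognostic in preliminary analyses, including adherence measures such as sleep and eating timing, and exercise". Body mass has no model of its own.

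Adherence is recorded while each condition is under way. Under Procedures, "The participants will also receive food, sleep, and exercise logs and actigraphs, which they will use for the study duration", and "Staff will send daily queries by text or e-mail to monitor adherence to the eating, sleep, and exercise parameters". Staff intervene the same day over, among other things, "eating or sleeping outside of the assigned time windows".

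The plan does not say how a covariate comes to be judged prognostic, which model or threshold does the screening, or whether eating timing means clock time or departure from the window. It mentions intent-to-treat only in connection with expected dropout.

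**The concern.** A covariate measured after randomisation can be a consequence of the assigned condition. Adjusting for it then no longer estimates the effect of assignment.

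- **Eating timing as clock time.** The condition coefficient becomes the effect of assignment at a fixed eating time. That is not the primary question. Because clock time nearly duplicates condition, the standard error also grows sharply.
- **Eating timing as deviation from the window.** Adjustment does no harm if deviations are the same in both conditions. If they differ, the estimate moves away from the total effect whenever deviation affects weight or shares an unmeasured cause with it.
- **Sleep and exercise.** The design means to hold these constant, but departures during a condition may still result from it.
- **Selection.** With no stated rule, the primary result can turn on a choice made after the data are seen. If timing does affect weight, as the trial hypothesises, it is likely to look prognostic.

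**Working it through.** **The plan's own figure.** The Analysis Plan expects 80% completion, n = 16. This follows from the 20 randomised given in the monitoring plan: 0.80 × 20 = 16. From the 30 in the objectives it would be 0.80 × 30 = 24. Both are used below. There is no power calculation to reproduce.

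**Assumed inputs** (not in the documents): total effect 1.0 kg; SD of within-person differences 1.2 kg; conditions 2 to 5 h apart in eating time; within-condition timing SD 0.5 to 1 h; two-sided 5% test.

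**Method.** A 2×2 cross-over was simulated on period differences, with and without the timing covariate (20,000 runs per setting; 40,000 for unequal deviations).

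**Unadjusted.** SE = 1.2/√16 = 0.30 kg; mean estimate 1.0 kg; power 87%. With 24 completers, SE = 1.2/√24 = 0.245 kg and power 97%.

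**A. Clock time as covariate.** Large-sample variance inflation = 1 + gap²/(2·SD²):

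- 2 h apart, SD 1 h: 1 + 4/2 = 3
- 5 h apart, SD 0.5 h: 1 + 25/0.5 = 51

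The simulated SE is about 1.5 to 8 times the unadjusted one.

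| Share of effect acting through timing | Mean adjusted estimate | Rejection rate |
|---|---|---|
| All | about 0 kg | 5% |
| Half | 0.5 kg | 6–15% |
| None | 1.0 kg | 7–40% |

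The last row is unbiased; its power is lost to collinearity alone. With 24 completers and the whole effect through timing, rejection is again 5% and the SE is 1.5 to 7.7 times larger.

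Fitting the plan's model form (REML, random subject, period, sequence, baseline; residual subject SD 0.5 or 1.5 kg; 1,000 runs per corner) with the whole effect through timing gave an adjusted estimate of −0.05 to 0.04 kg, rejection of 4–6% and an SE ratio of 1.3 to 7.4.

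**Screening first.** Assume timing enters only if p < 0.05, with the whole effect through timing. Power is 5–6% if the screening model omits condition and 32–85% if it includes condition.

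**B. Absolute deviation from the window, equal in both conditions.** Estimate 1.0 kg, power 84–85%.

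**C. Deviation larger in the delayed condition, sharing an unmeasured cause with weight change.** Let m be the difference in deviation (0.5 to 1 SD of the within-person deviation difference) and r its correlation with weight change (0.3 to 0.5). Expected bias = −r × 1.2 × m:

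- smallest: −0.3 × 1.2 × 0.5 = −0.18 kg
- largest: −0.5 × 1.2 × 1 = −0.60 kg

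With no true effect, false positives are 8–31%. With a true 1.0 kg, the estimate is 0.82 down to 0.40 kg and power 62% down to 16%.

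**Second set of assumptions.** With a within-subject SD of 0.9 kg, conditions 2 to 6 h apart and n = 16, clock-time adjustment (whole effect through timing) gave −0.02 to 0.04 kg, and power fell from 82% to about 5%.

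**The case against.** The strongest reply is that the plan speaks of adherence measures, and Procedures describes eating-timing adherence as departure from a window. On that reading, with equal adherence, adjustment costs only a few points of power (B). This is the more natural reading, but the Analysis Plan does not state it, and it gives no protection when adherence differs by condition.

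Entry is also conditional. If the screening model contains condition, the 32% figure arises only at a 2 h gap with SD 1 h; the other seven settings give 63–85%. That stands: loss of the effect is possible, not certain. But the plan names no screening model, so the 5–6% case is equally open.

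Case C is demanding. The cross-over removes stable personal causes, so the unmeasured cause must vary between periods, and same-day intervention should limit deviations. Reversing the correlation would push the estimate up instead, to 1 + 0.18 = 1.18 kg through 1 + 0.60 = 1.60 kg. All this is fair, and it makes the direction of bias unknown rather than absent.

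The Abstract lists eating timing, sleep timing and exercise among the things controlled for. That may mean control by design; it does not make adjustment for the randomised factor valid. Sleep and exercise adjustment does have a rationale, and a supportive analysis can serve it.

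The 1.0 kg effect is only illustrative. A cited two-week cross-over study found −0.04 against +0.06 kg. The daily adherence questions are in an appendix not seen here and might define the windows.

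**Conclusion.** The concern holds, and the plan should be changed before analysis. The sole model for the primary outcome permits adjustment for consequences of randomisation, including the randomised factor, by an undefined data-driven rule. The stated intent-to-treat principle does not exclude this.

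The harm ranges from negligible (deviation coding, equal adherence) to complete loss of a true effect (clock time, whole effect through timing). Differential adherence with a shared cause can produce false positives in up to 31% of trials. These sizes rest on assumed inputs throughout, apart from the 16 completers. That the estimate can be distorted follows from the model as written and does not depend on those values.

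**What to change.** In the Analysis Plan, remove the adherence measures and the selection by preliminary analyses from the primary model. Specify body mass on assigned condition, period, sequence, baseline body mass and random subject. State which assessment supplies baseline; only the first precedes randomisation. Name any further covariate in advance and require that it be measured before randomisation.

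Report eating timing, sleep timing and exercise by condition. Keep adherence-adjusted models, including those for residual sleep and exercise departures, as labelled supportive analyses, and define each covariate's coding (clock time or deviation from window). The Abstract need not change.

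The cost is a few lines of analysis-plan wording. All adherence data are still collected and reported.
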